19 OUTCOME MEASURES

The baseline measures will be collected before randomization and the outcome assessments will blind. All assessment measures, will be collected by the same clinician who was not involved in the treatment programs. In addition, at the physiotherapy service patients received a paper copy of the questionnaires to fill out on their own.

The following patient-reported outcome measures were used to assess participants' shoulder pain and function: the Disabilities of Arm, Shoulder and Hand (DASH) score and the Constant-Murley (CM) score.

27 • Primary outcome measures

The DASH was taken as a primary outcome measure. It is one of the most widely used self-reported questionnaires that measures symptoms and degree of function related to a disorder in the upper extremity. It has been validated in Spanish and comprises 30 items: 21 about physical function, 6 for symptoms, and 3 to assess social aspects. In addition, there are two optional modules, each with four items, which are used to assess symptoms and function in those whose functional demands are not included in the main part of the questionnaire.

This instrument has been used in previous studies involving physical therapy and exercise for shoulder injuries. It is scored in two components: first the symptom questions (30 items) and second the optional modules. The assigned values for all completed responses are summed and averaged, producing a score that is then transformed on a scale of 0 to 100 by subtracting one and multiplying by . A higher score indicates greater disability. Differences in scores are considered clinically relevant (minimum clinically important difference or MCID) when they are above 10 points.

42 • Secondary outcome measures

The CM score is a commonly used specific instrument for assessing the shoulder joint.
The maximum score is 100 points, 90 to 100 being excellent, 80 to 89 good, 70 to 79

1 medium, and less than 70 poor, considering that the scores can vary with age. This tool 2 includes a subjective assessment of the patient's pain and ability to perform daily 3 activities (35 points) and an objective assessment of mobility and strength by physical 4 examination (65 points). Its use has been specifically validated in shoulder arthroplasty, 5 rotator cuff repair, adhesive capsulitis, and fractures of the proximal humerus, but not in 6 shoulder instability.

7

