7 STUDY DESIGN

8 A pilot feasibility study, single bling with two groups (experimental and control group). 9 Clinical outcome measures will be shoulder function and pain (Constant Murley Score 10 and Disabilities of the Arm, Shoulder, and Hand or DASH score). Each variable will be 11 measured by a blinded physiotherapist at baseline and at one month follow-up. Patients 12 performed the prescribed exercises either supervised by the physiotherapist (control 13 group) or in a separate room without therapist supervision (experimental group).

14

15 **Regarding the study population**.

16 Patients who will be referred to the rehabilitation service of the University Hospital of

17 Elche (Spain) for physiotherapy treatment (manual therapy, exercise, stretching, and

18 electrotherapy) after suffering orthopedic injury or surgery in the shoulder joint complex,

19 from July 2023 to December 2023 will be considered for enrollment in the study.

20 Inclusion criteria were established as follows:

- 21 (i) be at least 18 years old and be able to read and understand Spanish.
- 22 (ii) suffer a traumatic or degenerative shoulder injury, with or without surgical
 23 treatment.
- (iii) have a prescription for rehabilitative physical therapy that includes active exercises.
- 26

27 The exclusion criteria adopted were:

Patients were excluded if they had a concomitant injury on an upper extremity or the cervical spine at the time of participation or sequelae of previous injuries in the area.

30

31 Regarding sample size

The main objective of this study is to know whether a clinical trial will be feasible and to have an estimate of standard deviation, which will be used in the sample size calculation for the large-scale trial; to estimate the rate (proportion) of eligible people who are willing to participate, of participants who drop out of the trial, or of participants who comply with the assigned intervention. That is why the sample size could be between 20 and 40 participants.

38

39 **METHODOLOGY**

40 Following baseline examination, patients will be randomly assigned to either 41 physiotherapist-supervised exercise (control group) or monitoring by the eFisioTrack

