system (experimental group). Patients will perform the prescribed exercises either 1 2 supervised by the physiotherapist (control group) or in a separate room without therapist 3 supervision (experimental group). A system of codes (four last numbers of the patient's ID number) was assigned to each participant using a computerized application (Research 4 randomizer: www.randomizer.org). Clinical outcome measures were shoulder function 5 6 and pain (Constant Murley Score and Disabilities of the Arm, Shoulder, and Hand or 7 DASH score). Each variable was measured by a blinded physiotherapist at baseline and 8 at one month follow-up.

9 The intervention consists of the use of the eFisioTrack platform in the experimental group to perform active exercises as part of their shoulder rehabilitation. These were performed 10 independently by each patient in a hospital room, using the efisioTrack system without 11 supervision by the physiotherapist. The design and use of eFisioTrack has been assessed 12 for usability and was described as appropriate and technically feasible. The subjects will 13 14 be previously instructed in the use of the system in two 20-minute sessions. The type of 15 exercise and its parameters will be chosen and progressed considering the functional status of the patient and being similar to those executed under the physiotherapist's 16 17 supervision.

18

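### The plan applies assessor blinding to every outcome, but the primary DASH is self-completed by patients who can tell which arm they are in

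*Combined protocol and SAP*

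**What the plan says.** Study Design labels the trial single blind (misspelt), names DASH and Constant-Murley as the clinical outcomes, and says each variable will be "measured by a blinded physiotherapist at baseline and at one month follow-up". The Methods paragraph of the Project Summary says the same, and the Methodology text repeats it: "Each variable was measured by a blinded physiotherapist at baseline and" at one month.

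Outcome Measures adds that baseline is taken before randomization, that the outcome assessments will be blind, and that "All assessment measures, will be collected by the same clinician who was not involved in the treatment programs". It then says that "patients received a paper copy of the questionnaires to fill out on their own".

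The same section states "The DASH was taken as a primary outcome measure" and places DASH among "self-reported questionnaires that measures symptoms and degree of function related to a disorder in the upper extremity". It introduces both DASH and Constant-Murley as patient-reported. It then splits Constant-Murley into 35 points for the patient's own view of pain and daily activities and 65 points for "an objective assessment of mobility and strength by physical" examination.

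On allocation, control patients exercise under a physiotherapist. Experimental patients exercise in a separate room, without a therapist, using eFisioTrack after two 20-minute instruction sessions. No sham, patient masking or concealment of the hypothesis is described.

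**The concern.** For a self-completed questionnaire the rater is the patient. A clinician who does not know the allocation can hand out, collect and score the form without bias, but the answers still come from someone who knows how they were treated. The plan therefore attributes to its primary comparison a protection that the comparison does not have.

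The stake is how the between-group DASH result is read. A difference could come from shoulder function or from expectation, such as the novelty of a device or disappointment at having no therapist. The direction of any such effect is unknown. Statistical Analysis plans a between-group t-test at P < 0.05 and does not acknowledge the issue. Because the pilot is meant to inform a larger trial, the same blinding statement could be carried forward.

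**Working it through.** **Step 1: who rates what.** Setting the sections side by side:

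| Component | Rater, from Outcome Measures | What the assessor's blinding protects |
|---|---|---|
| DASH (primary) | Patient, on paper, alone | Handling and scoring of the form |
| Constant-Murley, 35 points | Patient's own view of pain and daily activities | Recording and scoring |
| Constant-Murley, 65 points | Examiner | The rating itself |

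**Step 2: can patients know their arm?** The plan has no sentence saying so. It follows from the design: one arm has a therapist present, and the other has a separate room, a device and device training. No other reading is plausible.

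**Step 3: which scores are exposed?** Baseline precedes randomization, so knowledge of allocation cannot affect it. The one-month score and the change from baseline are exposed.

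**Step 4: illustration of size.** The conclusion rests on Steps 1 to 3. What follows only gives a sense of scale.

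The plan states no DASH SD, so its 36 per group cannot be reproduced from its own inputs alone. Using n = 2(1.960 + 0.842)² SD² / 10² with SD 15 gives 2 × 7.85 × 225 / 100 = 35.3, rounded up to 36. So an SD near 15 fits, two-sided and without inflation. If the 20% sampling error in Statistical Analysis means attrition, SD 13.5 gives 29, and 29 / 0.8 rounds up to 37, so the SD is not settled. I use 15 to 20 as an assumed range.

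Assume no true effect, a reporting shift b between arms of 3 or 5 DASH points, and a two-sided 5% t-test. The values of b are also assumptions; 5 is half of the 10-point clinically important difference in Outcome Measures. The planned total of 20 to 40 participants gives 10 to 20 per arm under equal allocation.

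Standard error = SD × √(2/n). Non-centrality = b / standard error. The rejection probability comes from the non-central t with 2n − 2 degrees of freedom. Example: n = 20, SD 15, b = 5 gives a standard error of 15 × √0.1 = 4.74, a non-centrality of 1.05, and a rejection probability of 17.7%.

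| Per arm | SD | Shift 3 | Shift 5 |
|---|---|---|---|
| 10 | 15 | 7.1% | 10.9% |
| 10 | 20 | 6.2% | 8.3% |
| 20 | 15 | 9.5% | 17.7% |
| 20 | 20 | 7.5% | 12.0% |

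A normal approximation gives similar values, for example 7.6% in place of 7.5%.

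**The case against.** The strongest reply is that nothing false is claimed. The trial is called single blind, the blinded role is the assessor, and Outcome Measures openly says DASH is self-reported. An uninvolved clinician who collects and scores forms is one consistent reading. Self-report cannot be avoided with this instrument, and the sample size paragraph puts feasibility first.

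Much of this stands. A reader might infer that the plan claims patient blinding; it does not. A reader might infer that it conceals the examiner-rated part of Constant-Murley by calling the score patient-reported. That label is loose, but the 35/65 split is stated in the same section. Nor do the documents show what a future report will say.

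A reader might also quote the much higher error rate at 36 per arm: 28.6% with SD 15 and a 5-point shift. That size is described as theoretical, and the planned total is 20 to 40. All these rates depend on an assumed SD and an assumed shift.

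A further tempting step is to treat a DASH difference as reporting bias unless the examination sub-score moves the same way. This does not work. Higher DASH is worse and higher Constant-Murley is better, so a real benefit moves them in opposite directions. Even with signs aligned, discordance at 10 to 20 per arm can be chance, and the two measures cover different content. Mobility and strength tests can also depend on the effort of a patient who knows the arm.

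What the reply does not answer is the wording itself. Measurement by a blinded physiotherapist is asserted for each variable without exception, in text that names DASH. The feasibility argument lowers the stakes but does not remove them, because Objectives gives the effect on clinical variables as the main aim.

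**Conclusion.** The point holds in a limited form. The blinding statement is wrong for the DASH answers, which are the whole of the primary outcome, and for 35 of the 100 Constant-Murley points. It is sound for form handling and scoring and for the 65 examiner-rated points. That patients know their arm is an inference, though a firm one.

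The documents do not show that reporting bias will occur, how large it would be, or which arm it would favour. At the planned size, the assumed SDs and shifts give error rates of 6.2% to 17.7% against a nominal 5%; these are illustrations, not estimates. The consequence is for the description and interpretation of the primary comparison. DASH need not be replaced as the primary outcome.

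**What to change.** 1. In the Project Summary, Study Design, Methodology and Outcome Measures, restrict the blinding statement to the examiner-rated Constant-Murley items and to handling and scoring of forms. State that DASH and the 35 subjective Constant-Murley points are reported by unblinded patients. Stop listing the whole Constant-Murley score as patient-reported. Require the between-group DASH result to be reported and interpreted as an unblinded comparison.
2. Keep DASH as primary. Pre-specify the 65-point examination sub-score as a supporting, descriptive outcome: between-group difference with 95% CI and no separate significance claim. Note that it is assessor-blind but still depends on patient effort.
3. Do not add a rule that attributes a DASH difference to reporting bias on the basis of agreement or disagreement with the sub-score.

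The cost is a less favourable description of the blinding and one more descriptive analysis of data already collected. No new data, visits or clinical changes are needed.

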8 SECURITY CONSIDERATION

9 The risks of the treatment techniques or manual therapy procedures as well as other means 10 of physical treatment and their possible adverse effects that will be used in this study are 11 uncommon and generally mild. Follow-up of cases with adverse effects will be 12 maintained until the end of the study. This measure ensures safe conditions for the 13 treatment of patients.

14

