28 EXPECTED OUTCOMES OF THE STUDY

29 This study aims to contribute to the advancement of the knowledge about the treatment

30 of acute grade II WL, showing the effectiveness of SAT technique compared to other

- 31 frequently used treatment protocols. The lack of randomized clinical trials related to the
- 32 application of spinal manipulation techniques in whiplash injury, compared to studies in
- 33 which passive and active interventions are applied, increases the interest of this study.
- 34

35 **PROJECT DURATION**

- 36 The study will be carried out in the buildings of the Rehabilitation Service at University
- 37 Hospital of Elche, starting in July 2023 and finishing in December 2023.
- 38

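### Adverse effects are only followed once they come to notice, while the randomised contrast removes the therapist from one arm's exercise sessions, so the pilot cannot compare harms fairly

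*Combined protocol and SAP*

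**What the plan says.** The Security Consideration section is one short paragraph. Its scope is given as "The risks of the treatment techniques or manual therapy procedures as well as other means" and, continuing the sentence, "of physical treatment and their possible adverse effects that will be used in this study are" described as rare and mostly mild. Its single procedure begins "Follow-up of cases with adverse effects will be" and runs to the end of the study. It then concludes: "This measure ensures safe conditions for the" treatment of patients.

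The contrast under test is set out in Study Design and Methodology. Patients are randomised to "physiotherapist-supervised exercise (control group) or monitoring by the eFisioTrack" system. Controls exercise under the physiotherapist. The other group exercises "in a separate room without therapist supervision (experimental group"), and Methodology adds that this is done "independently by each patient in a hospital room, using the efisioTrack system without" a physiotherapist supervising.

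Outcome Measures lists the DASH (primary) and the Constant-Murley score (secondary), taken at baseline and one month by a blinded assessor, with questionnaires also given to patients on paper to complete themselves. Statistical Analysis plans means, standard deviations, a normality test and t-tests. Neither section mentions adverse events.

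**The concern.** Following up known cases is not a way of finding cases. The protocol does not say what counts as an adverse effect, who asks about it, when, or where it is recorded. Detection therefore depends on a patient volunteering a problem or on someone seeing it. The person best placed to see a problem during exercise is the supervising physiotherapist, and that person is absent from one arm by design.

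If true harm were the same in both arms, fewer session-related events would then be expected to come to light in the experimental arm. Any such imbalance would flatter unsupervised use. The Project Summary looks ahead to home-based rehabilitation and a lighter physiotherapy workload, so readers will want to know whether exercising without supervision was tolerated. This plan could not tell them.

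**Working it through.** The protocol gives no adverse-event rate and no safety calculation, so there is no figure to reproduce. The check sets the ways in which a harm could come to notice side by side.

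| Route to detection | Control | Experimental | Source |
|---|---|---|---|
| Physiotherapist supervising the exercise | Yes | No | Study Design, Methodology |
| Hospital premises | Yes | Yes | Methodology, Project Duration |
| Contact through other referred physiotherapy | Yes, frequency not stated | Same | Study Design |
| Review when exercises are chosen and progressed | Yes | Yes, reviewer and frequency not stated | Methodology |
| Blinded DASH and Constant-Murley at one month | Yes | Yes | Outcome Measures |
| Planned question about adverse events | None | None | Security Consideration, Outcome Measures |

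Only the first row differs between arms, and it is the randomised contrast. The last row, which could make detection equal, is empty in both arms. The one-month scores would reflect lasting pain or lost function equally. They would not identify an event that had resolved, or link one to an exercise session.

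**Illustration only.** Let p be the true proportion of patients harmed, s the share of harms recorded, and n the number per arm. All values of p and s are assumptions. The sample-size paragraph in Study Design gives 20 to 40 participants in total; assuming 1:1 allocation, n = 20/2 = 10 to 40/2 = 20.

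Chance of recording at least one case in an arm = 1 − (1 − p·s)^n.

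| n | p | s = 1 | s = 0.5 | s = 0.25 |
|---|---|---|---|---|
| 20 | 10% | 1 − 0.90^20 = 88% | 1 − 0.95^20 = 64% | 1 − 0.975^20 = 40% |
| 10 | 10% | 1 − 0.90^10 = 65% | 1 − 0.95^10 = 40% | 1 − 0.975^10 = 22% |
| 20 | 5% | 1 − 0.95^20 = 64% | 1 − 0.975^20 = 40% | 1 − 0.9875^20 = 22% |

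If true rates are equal and recording is complete in the control arm, the expected apparent ratio of experimental to control harms is (p·s)/p = s. With s = 0.5 the unsupervised arm appears to have half the harms. This shows how the mechanism works. It does not estimate its size in this trial.

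**The case against.** The strongest reply is that this is a small pilot with no safety objective, in a hospital, with treatments the protocol regards as low risk, and that harms have several routes to notice in both arms. Much of that stands:

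- **Scope.** A reader might infer that the safety section covers manual therapy alone. It does not: its wording extends to other physical treatment used in the study, which can include exercise. What holds is that unsupervised exercise and eFisioTrack are never named.
- **Leftover text.** The Expected Outcomes section refers to the "application of spinal manipulation techniques in whiplash injury, compared to studies in" which other interventions are applied. It is tempting to conclude that the safety section was also carried over from another protocol. The documents do not show this: manual therapy is part of the referred care listed in Study Design. The whiplash text is a separate matter.
- **Consequence for the main trial.** A reader might infer that a wrong harm figure passes to the large-scale trial. Study Design lists what is to be estimated: a standard deviation and the rates of willingness, dropout and compliance. No harm rate is among them.
- **Zero events.** One might argue that no events among 10 or 20 patients leaves exact two-sided 95% upper limits of 1 − 0.025^(1/10) = 31% or 1 − 0.025^(1/20) = 17%. The arithmetic is right, but it describes small-sample imprecision, which would remain with perfect detection and which the fix does not change.
- **Nobody present.** The text excludes supervision by the physiotherapist. It does not say that no other staff are nearby.

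There is also a fair objection to the remedy. A blinded assessor who takes event histories may learn that a patient exercised alone with the device, and 65 of the 100 Constant-Murley points come from physical examination. The order of questioning can deal with most of this.

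None of these points supplies a planned, identical way of finding events in both arms.

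**Conclusion.** The concern holds in a limited form. The plan follows only adverse effects already known, does not collect or analyse events, and does not mention the contrast it is testing when it discusses safety. Transient or session-related harms are likely to be noticed less often in the experimental arm. That is an inference about direction, resting on the absence of a therapist during exercise; its size cannot be derived from the documents. Lasting pain or loss of function would still be seen in both arms at one month.

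As written, the pilot could give no fair comparison of harms, and passive follow-up does not support the assurance about safe conditions. The primary DASH analysis is not affected. The change should be made because it is cheap and better than passive follow-up.

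**What to change.** - Add adverse events as a descriptive outcome, with a short definition.
- Put the same few questions (for example increased pain, new injury, fall, other) to every patient in both arms at the existing one-month visit. Place them on the paper form that patients complete themselves, or ask them only after the DASH and Constant-Murley have been scored, so that scoring stays blinded.
- Include patients who withdraw early, where they can be reached, since some may have left because of a harm.
- In Statistical Analysis, report the number of patients with events by arm with exact 95% confidence intervals and no hypothesis test.
- In Security Consideration, name unsupervised exercise with eFisioTrack as the contrast, and remove the statement that follow-up ensures safe conditions.

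The cost is a little more data entry and one table. Two limits remain: answers rely on one month's recall, and there is a small risk of unblinding that the ordering reduces. Clinical handling of events is left to the investigators.
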